6.3.3.17 Electrolyte Disorders

Serum electrolyte disorders including hyponatremia, hypokalemia, hypomagnesemia, and hypophosphatemia have been reported during treatment with cabozantinib, and serum electrolyte levels should be monitored frequently while receiving cabozantinib. Clinically relevant electrolyte disorders should be managed according to the dose modification guidelines as outlined in Section 6.3 or as clinically indicated. Standard clinical practice guidelines should be used for management of electrolyte disorders and may include oral or intravenous replacement.

6.3.3.18 Endocrine Disorders

Treatment-emergent elevation of thyroid-stimulating hormone (TSH) has been observed with cabozantinib treatment. Currently available data are insufficient to determine the mechanism of thyroid function test alterations and its clinical relevance. Management of thyroid dysfunction (eg, symptomatic hypothyroidism) should follow accepted clinical practice guidelines.

6.3.3.19 Angioedema

Angioedema should be managed according to standard practice. The subject should be observed until symptoms resolve, with particular attention to maintaining an open airway.

7 CONCOMITANT MEDICATIONS AND THERAPIES

7.1 Allowed Therapy

- Antiemetics and antidiarrheal medications are allowed prophylactically according to standard clinical practice if clinically indicated.
- Granulocyte colony-stimulating factors (G-CSF or GM-CSF) are allowed if used per clinical guidelines (eg, ASCO or ESMO guidelines).
- Bisphosphonates can be used to control bone loss or hypocalcemia if the benefit outweighs the risk per the investigator's discretion.

Note: osteonecrosis of the jaw has been reported in subjects using bisphosphonates (Section 6.3.3.8). Oral examinations are recommended at screening to determine eligibility and periodically during the study. In addition, subjects should be advised regarding oral hygiene practice and to quickly report symptoms to the investigator. Frequent monitoring for potentially overlapping toxicities with study treatment is recommended.

- Transfusions and hormone replacement should be utilized as indicated by standard clinical practice.
- Individualized anticoagulation therapy with heparin is allowed if it can be provided safely and effectively under the following circumstances:
 - *Low dose heparins for prophylactic use* are allowed if clinically indicated and the benefit outweighs the risk per the investigator's discretion.
 - *Therapeutic doses of LMWH at the time of the first dose of study treatment* are allowed if the subject has no evidence of brain metastasis, has been on a stable dose of LMWH for at least 6 weeks, and has had no complications from a thromboembolic event or the anticoagulation regimen.
 - *Therapeutic doses of LMWH after first dose of study treatment* are allowed if clinically indicated (eg, for the treatment of deep venous thrombosis), and the benefit outweighs the risk per the investigator's discretion. For management of thromboembolic complications while on study, refer to Section 6.3.3.4.
 - Accepted clinical guidelines regarding appropriate management while receiving anticoagulation therapy with heparins must be followed. This includes, but is not limited to, subject education regarding potential adverse drug reactions, monitoring laboratory parameters, dose adjustments (eg, due to kidney dysfunction).
 - For restrictions on oral anticoagulants see Section 7.2.

Potential drug interactions with cabozantinib are summarized in Section 7.3.1.

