5.5 Laboratory Assessments

Laboratory panels are composed of the following:

Hematology		

 WBC count with differential (including at minimum: neutrophils, basophils, eosinophils, lymphocytes, monocytes) 	
 hematocrit platelet count RBC count hemoglobin 	
Serum chemistry		

 albumin ALP amylase ALT AST bicarbonate BUN chloride 	
 creatinine GGT Glucose (fasted) calcium lactate dehydrogenase lipase CRP 	
 magnesium phosphorus potassium sodium total bilirubin total protein
Urinalysis		

 appearance color pH specific gravity ketones protein UPCR 	
 glucose bilirubin nitrite creatinine urobilinogen 	
 occult blood (microscopic examination of sediment will be performed only if the results of the urinalysis dipstick evaluation are positive)
Other		

 TSH, Free T3 and Free T4 Pregnancy text (urine or serum) for women of child-bearing potential 		
 PT/INR or PTT

ALP, alkaline phosphatase; ALT, alanine aminotransferase; AST, aspartate aminotransferase; BUN, blood urea nitrogen; ESR, erythrocyte sedimentation rate; GGT, γ -glutamyltransferase; INR, International Normalized Ratio; PT, prothrombin time; PTT partial thromboplastin time; RBC, red blood cell; TSH, thyroid stimulating hormone; UPCR, urine protein/creatinine ratio; WBC, white blood cell; CRP, C-reactive protein

Abnormalities in clinical laboratory tests that lead to a change in subject management (eg, dose delayed [withheld] or reduced, requirement for additional medication, treatment or monitoring) are considered clinically significant for the purposes of this study, and will be recorded on the Adverse Events Case Report Form (CRF). If laboratory values constitute part of an event that meets criteria defining it as serious, the event (and associated laboratory values) must be reported as an SAE.

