6.3.3 Cabozantinib

The most frequent AEs experienced by $\geq 20\%$ of subjects treated with cabozantinib in descending order of frequency were diarrhea, fatigue, decreased appetite, nausea, weight decreased, PPES, vomiting, constipation, hypertension, dysgeusia, dysphonia, asthenia, and dyspnea. For a full description of the safety profile of cabozantinib, refer to the Cabozantinib Investigator's Brochure.

Other medically important but less frequent AEs including arterial thrombotic AEs (eg, transient ischemic attack [TIA], and myocardial infarction [MI]) and venous thrombotic AEs (eg, deep vein thrombosis [DVT] and pulmonary embolism), severe hemorrhagic events, proteinuria, wound healing complications, gastrointestinal (GI) perforation, abscesses including intra-abdominal and pelvic abscess, GI and non-GI fistula formation, osteonecrosis, and reversible posterior leukoencephalopathy syndrome (RPLS).

Adverse events associated with laboratory abnormalities experienced by $\geq 5\%$ of subjects treated with cabozantinib in descending order of frequency were anemia, AST increased, ALT increased, hypothyroidism, hypokalemia, hypomagnesemia, thrombocytopenia, hypocalcemia, hypophosphatemia, lactate dehydrogenase (LDH) increased, lipase increased, neutropenia, hyponatremia, ALP increased, leukopenia, and hyperglycemia.

Adverse events may occur within the first few weeks in the course of treatment with cabozantinib, as cabozantinib is expected to reach steady state exposure at approximately 2 weeks following first dose. Events that generally have an early onset include hypocalcemia, hypokalemia, thrombocytopenia, hypertension, PPES, abdominal pain, mucosal inflammation, constipation, diarrhea, and vomiting. Adverse events should be managed with supportive care at the earliest signs of toxicity. Dose reductions and treatment interruptions should be considered. Dose reductions are recommended for events that, if persistent, could become serious or intolerable (Section 6.3).

Cabozantinib should be discontinued for the following AEs: visceral perforation or fistula formation, severe hemorrhage, serious arterial thromboembolic events, nephrotic syndrome, hypertensive emergency, persistent uncontrolled hypertension despite optimal medical management, and RPLS.

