6.3.3.16 Corrected QT Prolongation

The effect of orally administered cabozantinib 140 mg qd on QTc interval was evaluated in a placebo-controlled study in subjects with MTC. A mean increase in QTcF of 10-15 ms was observed after 4 weeks after initiating cabozantinib treatment. A concentration-QTc relationship could not be definitively established. Changes in cardiac wave form morphology or new rhythms were not observed. No cabozantinib-treated subjects in this study had a QTcF > 500 ms. Review of the larger safety database (~5000 subjects exposed to cabozantinib in clinical trials and in post-marketing experience) confirmed the absence of safety concerns associated with QT prolongation. There were no events of torsades de pointes reported.

Concomitant treatment with strong cytochrome P450 (CYP) 3A4 inhibitors, which may increase cabozantinib plasma concentrations, should be avoided.

If at any time on study there is an increase in QTcF to an absolute value > 500 ms, two additional ECGs must be performed with intervals not less than 3 min apart within 30 min after the initial ECG.

If the average QTcF from the three ECGs is > 500 ms, the following actions must be taken:

- Interrupt cabozantinib treatment
- Hospitalize symptomatic subjects (eg, with palpitations, dizziness, syncope, orthostatic hypotension, a significant ventricular arrhythmia on ECG) for a thorough cardiology evaluation and management
- Consider cardiology consultation for asymptomatic subjects for evaluation and management
- Check electrolytes, especially magnesium, potassium and calcium; correct abnormalities as clinically indicated
- Check concomitant medications for any medication that may have contributed to QT prolongation, and if possible, discontinue these medications (<http://www.qtdrugs.org>)

- Repeat ECG triplicates hourly until the average QTcF is ≤ 500 msec, or otherwise determined by consultation with a cardiologist or appropriate expert.

Subjects with QTc prolongation and symptoms must be monitored closely until the QTc elevation and symptoms have resolved. Cabozantinib treatment may be restarted at a reduced dose level if all of the following conditions are met:

- Symptoms are determined to be unrelated to the QT interval prolongation
- The QTcF value > 500 ms is not confirmed
- Cabozantinib treatment has been interrupted through a minimum of 1 week following the return of the QTcF to ≤ 500 ms.

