8.2 Other Safety Considerations

8.2.1 Laboratory Data

All laboratory data required by this protocol and any other clinical investigations should be reviewed. Any abnormal value that leads to a change in subject management (e.g., dose reduction or delay or requirement for additional medication or monitoring) or that is considered

to be of clinical significance by the investigator should be reported as an AE or SAE as appropriate.

8.2.2 *Pregnancy/Lactation Exposure*

If a subject becomes pregnant during the study, she will be taken off study treatment and will be followed through the end of her pregnancy. Pregnancy (in subject or partner) or lactation exposure, although not an SAE, should be reported to Exelixis. Forms will be provided to the study sites upon request. The outcome of a pregnancy (for a subject or for the partner of a subject) and the medical condition of any resultant offspring must be reported to Exelixis. Any birth defect or congenital anomaly must be reported as an SAE, and any other untoward events occurring during the pregnancy must be reported as AEs or SAEs, as appropriate.

8.2.3 *Medication Errors/Overdose*

Any overdose, or study drug administration error that results in an AE, even if it does not meet the definition of serious, requires reporting within one (1) business day to Exelixis.

8.2.4 *Follow-Up of Adverse Events*

Any related SAEs or any AEs assessed as related that led to treatment discontinuation, including clinically significant abnormal laboratory values that meet these criteria, ongoing 30 days after the decision to discontinue study treatment must be followed until either resolution of the event or determination by the investigator that the event has become stable or irreversible. This follow-up guidance also applies to related SAEs that occur more than 30 days after the decision to discontinue study treatment. The status of all other continuing AEs will be documented as of 30 days after the decision to discontinue study treatment.

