The DSMC will render a recommendation and rating based on the overall trial conduct. The PI is responsible for ensuring that instances of egregious data insufficiencies are reported to the IRB. Continuing Review submissions will include the DSMC recommendation letter. Should any revisions be made to the protocol-specific monitoring plan after initial DSMC approval, the PI will be responsible for notifying the DSMC of such changes. The Committee reserves the right to conduct additional audits if necessary.

[name] and the investigators, the clinical research coordinator and the regulatory affairs coordinator will meet to review and discuss study data to ensure subject safety. During the meetings the PI or co-I will review the eligibility criteria for each new patient. In addition, during these meeting the group will review all the toxicity (AE/SAE) logs, random checks of case report form completion and roadmap for each patient on the trial. All study personnel will be trained on the protocol by the PI or co-I. Study personnel will sign training log prior to being included on delegation of authority log. All AE and SAE will be handled according to Section 8.2 which provides detailed instructions on reporting requirements.

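### Section 7.1 lists hypocalcemia as a reason to give bisphosphonates, which lower calcium: a minor safety wording error, probably a slip for hypercalcemia

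*Combined protocol and SAP*

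**What the plan says.** Section 7.1 (Allowed Therapy) lists medicines that may be given alongside cabozantinib. One bullet reads "Bisphosphonates can be used to control bone loss or hypocalcemia if the benefit outweighs the risk", and leaves that judgment to the investigator. The note beneath it deals with osteonecrosis of the jaw, oral examination and hygiene, and monitoring for overlapping toxicity. It does not mention calcium.

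Section 6.3.3 mentions hypocalcemia twice as an effect of the study drug. It is in the list of laboratory adverse events seen in at least 5% of cabozantinib-treated subjects: "hypothyroidism, hypokalemia, hypomagnesemia, thrombocytopenia, hypocalcemia, hypophosphatemia, lactate dehydrogenase (LDH) increased". It is also the first item in the list of early effects: "Events that generally have an early onset include hypocalcemia, hypokalemia, thrombocytopenia".

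Two passages bear on how low calcium is handled. Section 6.3.3.17 says "Standard clinical practice guidelines should be used for management of electrolyte disorders and may include oral or intravenous replacement". Section 6.3.3.16, for a confirmed average QTcF above 500 ms, says "Check electrolytes, especially magnesium, potassium and calcium; correct abnormalities as clinically indicated".

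**The concern.** The two uses joined in the Section 7.1 bullet pull in opposite directions. Controlling bone loss is an ordinary purpose of an antiresorptive drug. Controlling low calcium is not, because the class reduces the release of calcium from bone and lowers the serum level. The sentence is complete and grammatical, and nothing suggests a redaction or a damaged table. It is also current operative text: sites would consult this list to see which medicines are allowed.

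What is at stake is patient safety, and only to a small degree. Taken literally, the bullet permits a calcium-lowering drug in a patient whose calcium has already fallen, possibly because of cabozantinib. No statistical quantity depends on the word.

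**Working it through.** No arithmetic tests this point. The check is whether the sentence is wrong as it stands, whether other text corrects it, and what limits its effect.

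1. **Is the sentence wrong?** The only input from outside the documents is that bisphosphonates lower serum calcium. This is undisputed class pharmacology, but it is an assumption in the sense that the protocol does not state it. Given that, hypocalcemia cannot be a sensible target for the class. Its pairing with bone loss makes hypercalcemia the likely intended word. That remains an inference.

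2. **Does other text correct it?** Bisphosphonates are mentioned in two places.
   - Section 7.1 contains the sentence itself and its note on the jaw.
   - Section 6.3.3.8 (Osteonecrosis) names them as a risk factor and urges caution. It gives no calcium-related use.

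   The word hypercalcemia does not occur in the protocol text available for review. Apart from Section 7.1, hypocalcemia occurs only in Section 6.3.3, as an adverse effect. Sections 6.3.3.16 and 6.3.3.17 do not mention bisphosphonates. Nothing corrects or explains the wording.

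3. **Could the situation arise?** Section 6.3.3 makes hypocalcemia an expected event. That shows the wording is relevant to this drug. It does not show how often an investigator would act on it, and the documents give no rate of bisphosphonate use for any purpose.

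4. **How many patients, and for how long?** Section 9 accrues 11 patients and then, if there is at least one response, 6 more: 11 + 6 = 17 at most. Sections 5.2 and 6.2 set treatment at 12 weeks. Exclusion criterion 1 (Section 4.2) removes patients with metastatic disease.

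5. **What stands between the wording and harm?**
   - The bullet permits and does not direct. It requires the investigator to judge that benefit outweighs risk.
   - Section 6.3.3.17 refers electrolyte disorders to standard guidelines and mentions replacement. Its list of disorders is introduced as examples, so low calcium is not shut out by being unnamed.
   - Table 5-1 (footnote b) puts calcium in the chemistry panel at screening, Week 1 Day 1, Week 2, Week 6 and the post-treatment visit, which is five scheduled tests.
   - Section 5.5 ("Abnormalities in clinical laboratory tests that lead to a change in subject management") and Section 8.2.1 ("Any abnormal value that leads to a change in subject management") make a laboratory abnormality that needs extra medication a recorded adverse event. Section 10 adds that at study meetings "the group will review all the toxicity (AE/SAE) logs".

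6. **Does it reach the result?** The primary endpoint is objective response at week 12, tested by the two-stage rule in Section 9. Neither the rule nor the endpoint refers to calcium or to bisphosphonates.

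**The case against.** The strongest reply is that this is an editorial slip that any physician would recognise. For harm to follow, an investigator would have to choose an antiresorptive for a low calcium and also judge that the benefit outweighed the risk, against the standard guidelines to which Section 6.3.3.17 points. In a short trial in non-metastatic disease there is little visible reason to use bisphosphonates at all. All of this stands, and it is why the point has the lowest severity. It does not make the sentence correct. The benefit-risk clause limits the damage from a wrong indication but does not justify naming one. Recording adverse events and reviewing logs come after the drug has been given.

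A reader might also infer more than the documents support:

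- **That Sections 7.1 and 6.3.3.17 conflict.** Section 7.1 is a discretionary permission, and Section 6.3.3.17 says that management may include replacement. They are not contradictory instructions. The tension comes from pharmacology.
- **That the management of low calcium is left open.** Section 6.3.3.17 covers electrolyte disorders in general, and Section 6.3.3.16 has calcium checked and corrected in the QTcF setting.
- **That the place of hypocalcemia in the adverse-event lists measures the risk.** It shows only that the event is expected.
- **That the replacement word is certain.** Confidence is high that the wording is wrong, and lower that hypercalcemia is what the authors meant.

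**Conclusion.** The point holds as a minor safety wording error. Section 7.1 names hypocalcemia as a use for a class of drugs that lowers calcium, hypocalcemia is an expected effect of the study drug, and no other text puts it right. The conclusion rests on the ordinary pharmacology of bisphosphonates, which the protocol does not state.

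Its size is small and cannot be expressed as a probability from the documents. Exposure is bounded by 17 patients and 12 weeks of treatment, and practical harm is unlikely. The matter is one of wording and not of trial design: sample size, error rates, endpoint and analysis are untouched.

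**What to change.** In Section 7.1, delete the words *or hypocalcemia*, or replace *hypocalcemia* with *hypercalcemia* if the study authors confirm that this was intended. Deletion needs no assumption about what was meant. No change to Section 6.3.3.17 is needed.

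The text change is one or two words, with a note to sites. Visits, sample size and analysis stay as they are. The cost includes an approval step. Section 13 requires Exelixis to review and approve modifications before they are implemented, and requires IRB/EC approval. Its exceptions from prior approval cover immediate hazards and purely logistical or administrative changes. A change to a permitted use of a drug may not qualify as administrative. Including the correction in the next amendment is proportionate.

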7.2 Prohibited or Restricted Therapy

The following therapies are prohibited until study treatment has been permanently discontinued:

- Any investigational agent or investigational medical device.
- Oral anticoagulants (eg, warfarin or other coumarin-related agents, direct thrombin or direct FXa inhibitors, or antiplatelet agents such as clopidogrel, or chronic use of aspirin above low dose levels for cardioprotection per local applicable guidelines).
- Any nonprotocol systemic anticancer treatment (eg, chemotherapy, immunotherapy, radionuclides, drugs or herbal products used specifically for the treatment of the cancer under investigation).

The following therapies should be avoided until study treatment has been permanently discontinued or until otherwise specified:

- Local anticancer treatment including palliative radiation, ablation, embolization, or surgery with impact on tumor lesions should not be performed until radiographic progression per RECIST 1.1 has been established.
- Erythropoietic stimulating agents (eg, epoetin alfa and darbepoetin alfa) should not be used based on a report of increased risk of tumor recurrence/progression associated with erythropoietin (Wright et al 2007).
- Concomitant medications that are known to prolong the QTc interval should be avoided in subjects who receive cabozantinib until they have permanently discontinued cabozantinib treatment (refer to <http://www.qtdrugs.org> for a list of drugs which have the potential to prolong the QTc interval).
- Chronic co-administration of cabozantinib with strong inducers of the CYP3A4 family (eg, phenytoin, carbamazepine, rifampin, rifabutin, rifapentine, phenobarbital, and St. John's Wort) may significantly decrease cabozantinib concentrations and should be avoided. Selection of alternate concomitant medications with no or minimal CYP3A4 enzyme induction potential is recommended.
- Caution must be used when discontinuing treatment with a strong CYP3A4 inducer in a subject who has been concurrently receiving a stable dose of cabozantinib, as this could significantly increase the exposure to cabozantinib.
- Co-administration of cabozantinib with strong inhibitors of the CYP3A4 family (eg, boceprevir, conivaptan, posaconazole, ketoconazole, itraconazole, clarithromycin, atazanavir, indinavir, nefazodone, nelfinavir, saquinavir, ritonavir, lopinavir, telaprevir, telithromycin, and voriconazole) may increase cabozantinib concentrations and should be avoided. Grapefruit, star fruit, and Seville oranges may also increase plasma concentrations of cabozantinib and should be avoided.

Additional information on potential drug interactions with cabozantinib is provided in Section 7.3.1.

